## 6. GENERAL CONSIDERATIONS FOR DATA ANALYSES

Data will be presented using descriptive statistics. For categorical variables, the number and percentage of subjects in each category will be presented. For continuous variables, the number of subjects [n], mean, standard deviation [SD], median, minimum, and maximum will be presented. All data will be presented in listings (including unscheduled visits).

In general, missing data will not be imputed, except for methods for handling missing data specified in Appendix 2.

### 6.1 SUBJECT POPULATIONS

#### 6.1.1 Screened Population

The Screened Population Set includes any subject who signed the informed consent form.

#### 6.1.2 Safety Analysis Set

**Safety Analysis Set Part A:** The Safety Analysis Set Part A consists of all subjects who have completed at least one blood or urine sample collection in Part A (from Scheduled or Unscheduled visits).

**Safety Analysis Set Part B:** The Safety Analysis Set Part B consists of all subjects who have completed at least one blood or urine sample collection in Part B (from Scheduled or Unscheduled visits).

The **Safety Analysis Set** consists of all subjects who are part of the Safety Analysis Set Part A and/or Part B.

#### 6.1.3 Full Analysis Set (FAS)

**FAS Part A:** The FAS Part A consists of all subjects who are screen success and who have at least one measure of buprenorphine or norbuprenorphine concentration in plasma or at least one measure of buprenorphine or norbuprenorphine concentration in urine (as free drug or from quantitative UDS) or at least one measure for buprenorphine qualitative UDS in Part A (from Scheduled or Unscheduled visits).

**FAS Part B:** The FAS Part B consists of all subjects who met continuation criteria for Part B and who have at least one measure of buprenorphine or norbuprenorphine concentration in plasma or at least one measure of buprenorphine or norbuprenorphine concentration in urine (as free drug or from quantitative UDS) or at least one measure for buprenorphine qualitative UDS in Part B (from Scheduled or Unscheduled visits).

The FAS consists of all subjects who are part of FAS Part A and/or FAS Part B.

#### **6.1.4 Pharmacokinetic Analysis Set**

The PK Analysis Set consists of all subjects who are screen success and who have at least one concentration measure for buprenorphine or norbuprenorphine in plasma or urine.

### **6.2 MULTIPLE COMPARISONS**

No statistical tests are performed for this study and thus no multiple comparisons are performed.

### **6.3 OTHER VARIABLE CATEGORIES TO PRESENT**

#### **Sex**

- Male
- Female

#### **Age categories**

- 18 - 44
- 45 - 64
- $\geq 65$

#### **Race**

- American Indian or Alaska Native
- Asian
- Black or African American
- Native Hawaiian or Other Pacific Islander

- White
- Other

**Ethnicity**

- Hispanic or Latino
- Not Hispanic or Latino

**Baseline body mass index (BMI) categories**

- Under weight:  $< 18.5 \text{ kg/m}^2$
- Normal:  $\geq 18.5 \text{ kg/m}^2$  and  $< 25 \text{ kg/m}^2$
- Over weight:  $\geq 25 \text{ kg/m}^2$  and  $< 30 \text{ kg/m}^2$
- Obese:  $\geq 30 \text{ kg/m}^2$

**6.4 DEFINITION OF STUDY DAY**

Study day is the day relative to the date of Visit 1 in Part A.

## 7. SUBJECT DISPOSITION

The number and percentage of subjects screened and considered as screen failures, if any, will be summarized. A listing of the inclusion/exclusion reasons for screen failures will be provided, if any.

The number and percentage of subjects in populations of Safety Analysis Set Part A, Safety Analysis Set Part B, FAS Part A and FAS Part B together with the number and percentage of subjects who completed Part A and the number of subjects who completed Part B will be summarized. The population in the Safety Analysis Set will be used as denominator to calculate the percentage. A completer for Part A is the subject in the Safety Analysis Set Part A who has completed all plasma and urine sample collections for Visit 1 (Scheduled or Unscheduled) for Part A. A completer for Part B is the subject in the Safety Analysis Set Part B who has completed all plasma and urine sample collections for Visits 2 and 3 (Scheduled or Unscheduled) in Part B. The reasons Part A subjects did not participate in Part B will be summarized.

If a subject completes Part B but does not complete Part A, a footnote will be added to clarify.

## 8. PROTOCOL DEVIATIONS

A protocol deviation (PDV) is any change, divergence, or departure from the study design or procedures defined in the protocol as per ICH E3 guidelines. Important PDVs are a subset of protocol deviations that may significantly impact the completeness, accuracy, and/or reliability of the study data or that may significantly affect subject's rights, safety, or well-being.

A listing of PDVs, classified as important and not important, will be presented by subject using the Safety Analysis Sets. Except for important PDV defined as below, all other deviations are considered as non-important PDV:

- The subject was deemed eligible for the study but did not meet key inclusion criteria as listed below:
  - The subject participated in Study RB-US-13-0003 or both Studies RB-US-13-0003 and INDV-6000-301 and received at least 2 SC injections of SUBLOCADE.
  - The subject must be within 12 months to the last day of the 36th months post his or her last SUBLOCADE injection at the time of the Screening visit.
  - The subject did not provide the informed consent prior to the start of any study procedures.
- Subject was deemed eligible for the study but did not meet key exclusion criteria as listed below:
  - The subject received SUBLOCADE or any other long-acting buprenorphine product at any time after ending their participation in Study RB-US-13-0003 or Study INDV-6000-301.
  - The subject has taken any buprenorphine (prescribed or illicit) within 3 weeks prior to the Screening visit.
- Part B continuation criteria: The subject did not meet Part B continuation criterion but continued to Part B.

- The subject was not discontinued after reporting use of SUBLOCADE or any other long-acting buprenorphine product during the study as specified in protocol Section 5.5.

## 9. DEMOGRAPHICS CHARACTERISTICS

Demographic characteristics (sex, ethnicity, race, age [as continuous (Years) and categories of 18 - 44, 45 - 64,  $\geq 65$ ], weight [kg], height[cm] and body mass index [BMI as continuous ( $\text{kg}/\text{m}^2$ ) and categories of  $<18.5$  (underweight),  $\geq 18.5$ - $<25$  (normal),  $\geq 25$ - $<30$  (overweight),  $\geq 30$  (obesity)]) will be summarized using descriptive statistics by the cohorts of Part A and Part B within the Safety Analysis Set and the FAS respectively. Qualitative variables (sex, ethnicity, race, age categories, BMI categories) will be summarized using frequency count and percentage, while quantitative variables (age, weight, height, BMI) will be summarized using mean, SD, median, minimum, and maximum. Demographic data will also be listed for all subjects in the Safety Analysis Set; variables will be added to indicate if the subject belongs to Safety Analysis Set Part A, Safety Analysis Set Part B, FAS Part A and FAS Part B.

Per protocol, the Part B subjects should be a subset of Part A subjects. If this is violated, a footnote will be added to specify.

## 10. MEDICAL HISTORY

Medical history is collected from the end of previous participation in the latest SUBLOCADE study the subject participated in. The medical history will be coded using Medical Dictionary for Regulatory Activities (MedDRA) version 21.1 or later version available during study and summarized by the number and percentage of subjects in each System Organ Class (SOC), Preferred Term (PT) by the cohorts of Part A and Part B within the Safety Analysis Set. Subjects will be counted only once for each PT, only once at the System Organ Class (SOC), and only once at subject level for the counting of total number of subjects with a medical history term. Counts will be presented in descending frequency unless otherwise specified.

Medical history data will also be listed for all subjects in the Safety Analysis Set; variables will be added to indicate if the subject belongs to Safety Analysis Set Part A, Safety Analysis Set Part B, FAS Part A and FAS Part B.

## 11. PRIOR AND CONCOMITANT MEDICATIONS

Based on the study protocol, prior medications are not collected in the study.

Concomitant medications are all medications taken during the study (from first visit to the last visit in the study), including any prescribed medication-assisted treatment (methadone, naltrexone, buprenorphine), and will be captured. Of note, treatment initiation with any extended-release buprenorphine product will lead to study discontinuation.

Concomitant medications will be categorized by preferred term and drug category class, such as ATC classes 1, and/or 2 or 3, per World Health Organization Drug Dictionary [WHODRUG]), Concomitant medications will be summarized by the cohorts of Part A and Part B within the Safety Analysis Set. The number and percentage of subjects using each medication will be displayed together with the number and percentage of subjects using at least one medication. For a selected ATC class (for example, ATC Class 2), if the medication is not coded for that class, the value of “Unassigned” will be used in summary table and the “Unassigned” category is always presented in the last in the summary table.

The listing of concomitant medications will be provided for all subjects in the Safety Analysis Set. Variables will be added to indicate if the subject belongs to the Safety Analysis Set Part A, Safety Analysis Set Part B, FAS Part A and FAS Part B. A variable in the listing will indicate whether the medication was also a prior medication (start date prior to the date of Visit 1 in Part A).

## 12. SAFETY ANALYSES

### 12.1 ADVERSE EVENTS

Only adverse events (AEs) associated with study assessments and/or study conduct will be collected using the Adverse Event eCRF. If any of these AEs become serious AEs (SAEs), they will be reported to Indivior via the Safety Information Collection Form.

Adverse events associated with study assessments and/or study conduct (AE onsets on or after the first visit in this study) will be coded using the most up-to-date version of the MedDRA dictionary, and grouped by primary SOC. These events will be summarized with frequency and percentage, by SOC and PT, by the cohorts of Part A and Part B within the Safety Analysis Set, with separate summaries for all AEs, AEs related to study procedures (such as urine collection procedure or blood collection procedure), and serious AEs. The incidence of deaths will also be reported.

Since there is no study drug for this study, no treatment emergent AE is defined for this study.

A summary of AEs will be presented by the cohorts of Part A and Part B within the Safety Analysis Set, including the number and percentage of subjects reporting at least one AE, the number and percentage of subjects with the following:

- AE summary
- All AEs by SOC and PT
- All AEs by SOC, PT and severity
- SAEs
- SAEs by SOC, PT and severity

A breakdown of the number and percentage of subjects reporting each AE categorized by SOC and PT coded per the MedDRA dictionary version or later version available during study will be presented by the cohorts of Part A and Part B within the Safety Analysis Set. Note that counting will be by subject not by event, and subjects will be only counted once within each SOC or PT.

A summary of events reported, categorized by severity, will also be provided by the cohorts of Part A and Part B within the Safety Analysis Set. Subjects with multiple events within a SOC or PT will be counted under the category of their most severe event within that SOC or PT. A further tabulation of severe AE will be presented by SOC and PT.

Additionally, all AEs will be summarized by maximum severity (mild, moderate, or severe).

AE will also be listed for all subjects in the Safety Analysis Set, variables will be added to indicate if the subject belongs to the Safety Analysis Set Part A, Safety Analysis Set Part B, FAS Part A and FAS Part B.

#### **12.1.1 Serious Adverse Events**

SAEs will be summarized separately by SOC and PT by the cohorts of Part A and Part B within the Safety Analysis Set.

All SAEs recorded on the CRF will be listed for the Safety Analysis Set.

#### **12.1.2 Deaths**

Deaths occurring in the study will also be listed for the Safety Analysis Set.

### **12.2 CLINICAL LABORATORY PARAMETERS**

No laboratory data collected for this study.

### **12.3 VITAL SIGNS**

No vital sign data collected for this study

### **12.4 OTHER SAFETY VARIABLES**

#### **12.4.1 Pregnancy Test**

Pregnancy test results collected during the study will be listed for the Safety Analysis Set.

### 13. PHARMACOKINETIC ANALYSIS

A blood sample will be collected at each visit for the determination of buprenorphine and norbuprenorphine plasma concentrations. A urine sample will also be collected at each visit for the determination of free buprenorphine and free norbuprenorphine concentrations; the realization of a qualitative UDS for opioids, including buprenorphine; a quantitative UDS for buprenorphine, norbuprenorphine and naloxone; and the determination of creatinine concentration.

#### 13.1 DESCRIPTIVE ANALYSIS

The number and percentage of subjects with negative and positive results for buprenorphine on the qualitative UDS will be summarized for FAS Part A at Visit 1 and for FAS Part B across Visits 1, 2 and 3. Qualitative UDS results for opioids other than buprenorphine will be summarized in a similar way.

The number and percentage of subjects with negative results for **both** buprenorphine and norbuprenorphine based on quantitative UDS or free drug concentrations will be summarized for FAS Part A at Visit 1 and for FAS Part B across Visits 1, 2 and 3. Negative and positive results for each analyte will also be summarized (buprenorphine, norbuprenorphine and naloxone for quantitative UDS; buprenorphine and norbuprenorphine for free drug concentrations). A negative result will be any concentration below the lower limit of quantification (LLOQ). A positive result will be any quantifiable concentration.

As for urine, the number and percentage of subjects with negative results for **both** buprenorphine and norbuprenorphine concentrations in plasma will be summarized for FAS Part A at Visit 1 and for FAS Part B across Visits 1, 2 and 3. Negative and positive results for each analyte (buprenorphine, norbuprenorphine) will also be summarized. A negative result will be any concentration below the LLOQ. A positive result will be any quantifiable concentration.

For all above tables, missing data will not be imputed. For Visits 2 and 3, data associated with the reported use of illicit buprenorphine at the visit or the use of prescribed buprenorphine within 3 weeks of the assessment will be excluded from all the above summary statistics calculation for that visit only. Those excluded data, if any, will be indicated in the listings. With respect to Visit 1, no data should be excluded since meeting the exclusion criteria infers that there was no use of prescribed or illicit opioid use within 3 weeks prior to the Screening visit.

For the following descriptive analyses, the PK analysis set will be used. A graphical representation of buprenorphine and norbuprenorphine plasma/urine concentrations over time will be provided. Individual plasma/urine concentration-time data will be plotted using the time elapsed from the last SUBLOCADE dose. A solid line will be used to link concentrations from a same subject. Concentrations of buprenorphine and norbuprenorphine in urine (from quantitative UDS or free drug concentration assessments) will be presented with and without correction by creatinine concentration in urine (Appendix 4). The purpose of the correction by creatinine urine concentration is to correct for urinary dilution.

For plasma and urine (uncorrected) concentration-time plots, concentrations below the LLOQ will be imputed with the LLOQ value. Three symbols will be used for 1) quantifiable concentrations, 2) concentrations below the LLOQ and 3) quantifiable concentrations associated with the reported use of illicit buprenorphine at the visit or the use of prescribed buprenorphine within 3 weeks of the visit. For concentration-time plots representing buprenorphine or norbuprenorphine urine concentrations after correction with creatinine concentration in urine, concentrations below the LLOQ will not be imputed and will not be shown on the plots.

Norbuprenorphine-to-buprenorphine ratios will be calculated from quantifiable concentrations in plasma, quantifiable concentrations of free drug in urine, and quantifiable concentrations from quantitative UDS. Values will be reported in listings. Summary statistics (mean, SD, median, 5th and 95th percentiles, minimum, maximum) will be calculated by subgroups defined by the intake (yes/no) of prescribed or illicit buprenorphine. One subject may contribute to multiple observations (up to 3).

Relationships between plasma and urine drug concentrations measured on the same day will also be explored by calculating urine-to-plasma ratios for quantifiable concentrations of buprenorphine or norbuprenorphine. Urine drug concentrations corrected by creatinine concentration or uncorrected will both be used to derive those urine-to-plasma concentration ratios. Values will be reported in listings. Summary statistics (mean, SD, median, 5th and 95th percentiles, minimum, maximum) will be calculated by subgroups defined by the intake (yes/no) of prescribed or illicit buprenorphine. One subject may contribute to multiple observations (up to 3).

Finally, plots will be constructed to assess the consistency of norbuprenorphine-to-buprenorphine ratios and of urine-to-plasma concentration ratios over time, using the time elapsed from the last SUBLOCADE dose. A solid line will be used to link data from a

same subject. Different symbols will be used by subgroups defined by the intake (yes/no) of prescribed or illicit buprenorphine.

Equations for correction of buprenorphine or norbuprenorphine urine concentrations or urine-to-plasma concentration ratios with creatinine concentration in urine are presented in Appendix 4.

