**Rationale:**

Data indicate that after discontinuing SUBLOCADE™ (extended-release buprenorphine subcutaneous [SC] injection), patients may have detectable concentrations of buprenorphine in plasma and urine for 12 months or longer. The correlation between buprenorphine concentrations in plasma and in urine is currently unknown.

Since previous Phase II/III studies did not evaluate the pharmacokinetics (PK) of buprenorphine beyond 2 months after the last injection of SUBLOCADE, the purpose of the current study is to characterise the long-term plasma exposure to buprenorphine starting at least 12 months after the last injection of SUBLOCADE.

This study will also assess relationships between plasma drug concentrations, free drug concentrations in urine, and urine drug screen (UDS) results for buprenorphine from a diagnostic laboratory. The intent of the study is to provide refined guidance to patients and physicians with respect to long-term exposure to buprenorphine after stopping SUBLOCADE treatment.

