### **8.5 Appropriateness of Measurements**

All of the safety assessments in this protocol are standard. The PK assessments have been used for quantification of buprenorphine and norbuprenorphine concentrations in plasma in previous registration studies for SUBLOCADE. The PK assessments are being used to assess the long-term plasma exposure to buprenorphine after stopping SUBLOCADE treatment and to refine the existing population PK model of SUBLOCADE. Some of the UDS assessments were also used in these prior registration studies. Together with plasma concentration data, urine results will be used to evaluate the relationships between drug plasma concentrations, free drug concentrations in urine, and UDS results for buprenorphine from a diagnostic laboratory.

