### **5.2 EXPLORATORY**

The exploratory objectives of this study are the following:

- Refine pharmacokinetic (PK) model predictions for long-term plasma exposure to buprenorphine after stopping SUBLOCADE treatment, by developing a more robust population PK model for SUBLOCADE; and
- Assess relationships between drug plasma concentrations, free drug concentrations in urine, and UDS results for buprenorphine from a diagnostic laboratory.

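### SAP 13.1 never relates the qualitative UDS to plasma status, and discordant quantitative UDS–plasma pairs enter a joint summary only in one partial case

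*SAP*

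**What the plan says.** The exploratory objective in SAP 5.2 names three quantities to be related: "Assess relationships between drug plasma concentrations, free drug concentrations in urine, and UDS results for buprenorphine from a diagnostic laboratory". Protocol 8.5 repeats the intention: "urine results will be used to evaluate the relationships between drug plasma concentrations, free drug concentrations in urine, and UDS results for buprenorphine". The Rationale in the protocol synopsis gives the reason: "The correlation between buprenorphine concentrations in plasma and in urine is currently unknown". Protocol 1.4 counts clarification of how plasma relates to a positive UDS among the expected gains from the study.

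SAP 13.1 then plans the following:

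- **Qualitative UDS, one-way:** "The number and percentage of subjects with negative and positive results for buprenorphine on the qualitative UDS will be summarized for FAS Part A" (first visit), with a similar count in FAS Part B covering all three visits.
- **Quantitative UDS and free drug in urine, one-way:** counts for the same sets and visits, where negative means below LLOQ.
- **Plasma, one-way:** a matching table, with "Negative and positive results for each analyte (buprenorphine, norbuprenorphine) will also be summarized".
- **Within one matrix or assay:** "Norbuprenorphine-to-buprenorphine ratios will be calculated from quantifiable concentrations in plasma, quantifiable concentrations of free drug in urine, and quantifiable concentrations from quantitative UDS".
- **Plasma against urine on the same day:** explored by "calculating urine-to-plasma ratios for quantifiable concentrations of buprenorphine or norbuprenorphine".

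Values below LLOQ are set to the LLOQ only in the plasma and uncorrected urine concentration–time plots. Likelihood-based handling of such values (SAP 13.2.2) applies only to plasma in the population PK model.

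**The concern.** The practical question for a patient or physician is how often a UDS is positive when the drug can no longer be quantified in plasma, and how often the reverse occurs. That is a question about pairs of results in one subject at one visit. Separate tables give only the margins of the pairing. The ratio keeps only pairs that are quantifiable on both sides, so the discordant pairs are exactly the ones it cannot contain. The qualitative UDS has no concentration and cannot enter a ratio at all.

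At stake is an exploratory objective and one of the stated uses of the study. The primary endpoint is a plot of plasma concentrations and does not depend on this analysis, nor does the population PK model.

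**Working it through.** **1. Which planned outputs pair plasma with UDS?**

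| Output (SAP 13.1) | Pairs plasma with UDS? | Can show discordance? |
|---|---|---|
| Qualitative UDS counts | No | No |
| Quantitative UDS and free-drug counts | No | No |
| Plasma counts, FAS Part A, Visit 1 | No | No |
| Plasma counts, FAS Part B, Visit 1 | Yes, indirectly | UDS-positive/plasma-negative only |
| Plasma counts, FAS Part B, Visits 2–3 | No | No |
| Urine-to-plasma ratio | Yes, if urine concentration includes quantitative UDS | No: both values must be quantifiable |

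The fourth row follows from SAP 6.1.3: "The FAS Part B consists of all subjects who met continuation criteria for Part B and who have at least one measure" in Part B. The continuation criterion (Protocol 5.4) requires a quantifiable quantitative UDS and a negative naloxone result at Visit 1, so this table gives plasma status among UDS-positive subjects. It covers at most 30 subjects. It leaves out the qualitative UDS, UDS-positive subjects who do not enter Part B, and Visits 2 and 3.

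**2. What the margins leave open.** With n subjects, a UDS-positive and b plasma-positive, the UDS-positive/plasma-negative count lies between max(0, a − b) and min(a, n − b). The counts below are assumed, for illustration.

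- Qualitative UDS, Visit 1: n = 60, a = 22, b = 20 gives 22 − 20 = 2 up to min(22, 40) = 22. Suppose the Part B tables are also used (24 subjects, 18 UDS-positive, 16 plasma-positive). Part B gives 2 to min(18, 8) = 8. The other 36 subjects (4 and 4 positive) give 0 to 4. The total is 2 to 12.
- Quantitative UDS, Visit 1: n = 60, a = 30, b = 20 gives 10 to 30. If 24 enter Part B and 17 of them are plasma-positive, Part B is exact at 24 − 17 = 7. The other 36 subjects (6 UDS-positive, 3 plasma-positive) give 3 to 6. The total is 10 to 13.

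These are arithmetical limits, not expected uncertainty.

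**3. How large might discordance be?** SAP Table 1 gives k64 = 0.000510 per hour, so the half-life is ln 2 / 0.000510 / 24 = 56.6 days. This lies inside the 43 to 60 days in Protocol 1.2. For a typical subject after six 300 mg injections, Table 1 predicts about 0.11 ng/mL at 12 months and 0.000015 ng/mL at 36 months, roughly a 7,600-fold fall. Values below LLOQ are therefore likely to be common.

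I simulated 200,000 profiles from the Table 1 estimates and variances, for the two regimens in SAP 13.2.6. Assumptions: 28-day dosing interval, slow-release path only, no covariates, 19% proportional error (Table 1), additive error omitted, sampling uniform over 12 to 36 months. UDS status was plasma buprenorphine times a log-normal factor (log-SD 0.5 to 0.8), judged against a threshold 1, 3 or 10 times more sensitive than plasma. Expected UDS-positive/plasma-negative subjects per 60:

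| Regimen, plasma LLOQ (ng/mL) | 1-fold | 3-fold | 10-fold |
|---|---|---|---|
| 6 × 300 mg, 0.01 | 1.1–1.6 | 5.2–5.3 | 10.0–10.1 |
| 6 × 300 mg, 0.05 | 1.2–1.9 | 6.2 | 12.1–12.2 |
| 2 × 300 + 4 × 100 mg, 0.01 | 1.1–1.7 | 5.6 | 10.8–10.9 |
| 2 × 300 + 4 × 100 mg, 0.05 | 1.2–1.9 | 6.3–6.4 | 12.6–12.7 |

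The excess over the lower bound a − b was 1.1 to 1.9 at equal sensitivity, at most about 0.2 at 3-fold, and 0 at 10-fold. Under these assumptions, a reader who took the lower bound from the one-way tables would be within about 2 of 60. The tables alone would not tell the reader that this is so.

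**The case against.** The strongest reply has four parts.

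- **The named endpoints are covered.** Protocol 3 lists plots, ratios and model estimates, with no concordance table. Protocol 14.5 promises only exploration of plasma–urine relationships, and Protocol 14.1 allows unplanned analyses if they are identified as such. This stands as a reason for low severity. It does not show that the objective's UDS component is analysed.
- **The quantitative UDS is partly covered.** SAP 13.1 elsewhere counts quantitative UDS values as urine concentrations. If the ratio includes them, and if n is shown as SAP 6 says for continuous variables, then UDS-positive minus n gives the discordant count. This stands in part: the ratio text does not name quantitative UDS, its own list of statistics omits n, and the summary pools up to three visits per subject. The qualitative UDS gains nothing from this reading.
- **Nothing is hidden.** Values below LLOQ have their own plot symbol and all data are listed. That is true, but matching listings by hand is not a planned analysis.
- **The wide ranges are extremes.** This stands. A reader might infer from 2 to 22 or 10 to 30 that the one-way tables are close to uninformative. The simulation does not support that.

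A reader might also infer that limiting ratios to quantifiable pairs biases them. The documents do not support that claim, because any direction depends on how the assay LLOQs compare, and none is given. With a norbuprenorphine LLOQ one quarter of buprenorphine's, a true plasma ratio of 0.30 gives a complete-pair median of 0.29 to 0.31, which is negligible.

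**Conclusion.** The gap is real and narrow. As written, the plan never relates the qualitative UDS to plasma. For the quantitative UDS it gives discordant pairs no joint summary beyond the FAS Part B table at Visit 1. The plasma–UDS part of the exploratory objective is therefore not fully analysed.

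Its size cannot be derived from the documents. The figures of about 1–2 of 60 (equal sensitivity) and 10–13 of 60 (urine ten times more sensitive) rest on assumed LLOQs, an assumed urine model and Table 1 extrapolated to 36 months. In most of these cases the count lies near the lower bound from the planned tables. It would go too far to say that the plan contains no plasma–UDS link at all, or that the ratios or the primary results are compromised. Severity is low.

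**What to change.** Add to SAP 13.1 a same-visit cross-table of plasma status (below LLOQ or quantifiable) by qualitative UDS result and by quantitative UDS result. Present it for FAS Part A at Visit 1 and for FAS Part B at Visits 1, 2 and 3. Use the section's existing definitions of negative and positive and its existing exclusions for buprenorphine use at Visits 2 and 3. It is purely descriptive, so the plan's decision to compute no tests or confidence intervals is respected.

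Beside the ratio statistics, report how many pairs were left out because one or both values were below LLOQ.

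The cost is a few lines of SAP wording and one table shell. All inputs are already collected at every visit. The drawback is an extra table with some small cells.
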